2.1. Study Objective(s) and Endpoint(s)

Objectives	Endpoints
Primary Objectives	Primary Endpoints

 To characterise the dose response of nemiralisib administered in addition to SoC compared with placebo and SoC in participants diagnosed with an acute moderate or severe exacerbation of COPD 	
 Change from baseline in Clinic Visit trough forced expiratory volume in one second (FEV₁) at Day 84 measured post-bronchodilator
Secondary Objectives	Secondary Endpoints

 To characterise the dose response and efficacy of nemiralisib administered in addition to SoC compared with placebo and SoC in participants diagnosed with an acute moderate or severe exacerbation of COPD 	
 Rate of moderate and severe exacerbations over the 12-Week Treatment Period Time to next moderate/severe exacerbation following index exacerbation Change from baseline in Clinic Visit trough FEV₁ measured pre- and post-bronchodilator at Days 14, 28, 56, and 84 (Day 84: post-bronchodilator is the primary endpoint; pre-bronchodilator is a secondary endpoint) and at hospital discharge (only for participants who are hospitalized for the index exacerbation) Change from hospital discharge in clinic visit trough FEV₁ measured pre- and post-bronchodilator at Days, 14, 28, 56, and 84 (in participants hospitalized for index exacerbation only)

 To evaluate the treatment effect of nemiralisib in addition to SoC compared with placebo and SoC on symptoms indicative of an exacerbation and on health status using Patient-Reported Outcomes (PROs) in participants diagnosed with an acute moderate or severe exacerbation of COPD 	
EXAcerbations of Chronic Pulmonary Disease Tool (EXACT-PRO)
 
 Proportion of participants achieving the EXACT definition of recovery from the index exacerbation by Days 14, 28, 56, and 84 Time to recovery from index exacerbation Severity of subsequent HCRU-defined exacerbation(s) defined by EXACT 
COPD Assessment Test (CAT)
 
 Proportion of responders using the CAT at Treatment Days 28, 56, and 84, and following EXACT defined

Objectives	Endpoints

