7.2.1.1. Statistical analyses

The rate of exacerbations will be analysed using a Bayesian generalized linear model assuming a negative binomial distribution for the underlying exacerbation rate with a log link function. An offset to account for the length of time on treatment or in study, depending on the specified time-period, for each participant (as described above) will be included in the model as \log_e (length of time).

Non-informative priors will be used for all modelling parameters. Wherever possible conjugate priors will be utilised.

The median exacerbation rates for each dose arm per 12 weeks, along with the median ratio in exacerbation rates (nemiralisib/placebo) per 12 weeks for each dose, will be estimated and corresponding 95% HPD credible intervals presented. The probability that the true exacerbation rate ratio is less than 1, in addition to other values appropriately selected based on the data, will be presented.

Based on pharmacological predictions, the 500 mcg and 750 mcg doses are expected to result in similar levels of target inhibition and thus potentially translate to similar clinical benefit, therefore estimates of the exacerbation rates for pooled data from 500 mcg plus 750 mcg will also be presented.

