7.2.2.1. Statistical analyses

Time to next exacerbation will be analysed using a Bayesian Cox proportional hazards model with the “Efron” method for handling ties.

Kaplan-Meier (KM) estimates of the probability of exacerbation will also be presented.

Non-informative priors will be used for all modelling parameters. Wherever possible conjugate priors will be utilised.

The hazard ratio and corresponding 95% HPD credible intervals for each nemiralisib dose versus placebo will be presented. The probability that the true hazard ratio is less than 1, in addition to other values appropriately selected based on the data, will be presented.

Based on pharmacological predictions, the 500 mcg and 750 mcg doses are expected to result in similar levels of target inhibition and thus potentially translate to similar clinical benefit, therefore an estimate of hazard ratio for pooled data from 500 mcg plus 750 mcg nemiralisib doses versus placebo will also be presented.

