11. PHARMACOKINETIC / PHARMACODYNAMIC ANALYSES

If statistical analyses suggest an effect of nemiralisib on primary and other key clinical endpoints, an integrated longitudinal population dose/exposure versus clinical response on analysis key parameters including FEV₁ and exacerbation rate will be undertaken. Participant characteristics influencing the relationship will be evaluated.

Details of these analyses will be described in a separate CPMS RAP and results will be reported separately to the CSR.

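### The exacerbation endpoints sit under a dose-response objective, but the SAP fits no unconditional dose-response model to them; a supportive model would close the gap cheaply.

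*SAP*

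**What the plan says.** Section 2.1 states the secondary objective as "To characterise the dose response and efficacy of nemiralisib administered in addition to SoC compared with placebo and SoC". The first two endpoints listed under it are "Rate of moderate and severe exacerbations over the 12-Week Treatment Period" and "Time to next moderate/severe exacerbation following index exacerbation".

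- **Rate (7.2.1.1).** "The rate of exacerbations will be analysed using a Bayesian generalized linear model assuming a negative binomial distribution", with a log link and a log-time offset. The outputs are "The median exacerbation rates for each dose arm per 12 weeks, along with the median ratio in exacerbation rates (nemiralisib/placebo"), given by dose. On a stated pharmacological ground, "therefore estimates of the exacerbation rates for pooled data from 500 mcg plus 750 mcg will also be presented".
- **Time to event (7.2.2.1).** A Bayesian Cox model. "The hazard ratio and corresponding 95% HPD credible intervals for each nemiralisib dose versus placebo will be presented", with a pooled 500+750 mcg hazard ratio as well.
- **FEV1 under the same objective (7.2.3.1).** Post-bronchodilator values at the other visits get the dose-response model of 7.1.2 and a repeated measures model. Pre-bronchodilator values, and change from hospital discharge (7.2.4.1), get repeated measures only.
- **Displays (Appendix 11).** Dose-response tables (Example Shell 26) and plots (Example Shell 18) exist for FEV1 only. The exacerbation analyses use Example Shells 6 and 8, which show active versus placebo.
- **PK/PD (Section 11, Appendix 9).** A dose/exposure-response analysis that includes exacerbation rate is triggered "If statistical analyses suggest an effect of nemiralisib on primary and other key clinical endpoints". Appendix 9 adds a joint look at time to first exacerbation and FEV1 as a function of dose or exposure. Both are left to a separate plan and reported apart from the CSR.

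**The concern.** A dose-response objective asks how the effect changes with dose. A set of ratios to placebo, with dose as an unordered factor, leaves that to the reader's eye. The two-dose pool averages the top of the range and says nothing about the shape from 12.5 to 250 mcg.

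The one planned analysis that would describe the shape runs only once other analyses have suggested an effect. Its existence therefore depends partly on the less efficient per-dose comparisons, and a reader of the CSR would not see it. At stake are a stated objective with no assured analysis for two clinically important endpoints, and some precision that the ordering of the doses could supply.

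**Working it through.** **Side by side.** The objective in 2.1 asks for dose response and efficacy. Sections 7.2.1.1 and 7.2.2.1 give efficacy by dose and one pool. Section 11 and Appendix 9 give dose/exposure response, but conditionally and outside the CSR. No unconditional dose-response estimate for exacerbations remains in the plan.

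**Size.** The SAP gives no event rate, dispersion, sample size or precision for these endpoints, so there is no figure of its own to reproduce. All the inputs below are assumptions:

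- Rate μ = 0.35 per 12 weeks; dispersion k = 0.8.
- Allocation 300 placebo, 300 at 750 mcg, 100 in each other arm. The pattern comes only from mock Example Shell 35, which has no 12.5 mcg column (100 assumed there). Example Shell 3 shows 200 per arm, so neither is a trial fact.
- Equal per-participant variance of the log rate in all arms: v = 1/μ + k = 2.857 + 0.8 = 3.657.

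*Planned analyses,* SE = √[v(1/n₀ + 1/n_d)]:

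- 100-participant arm: √[3.657 × (1/300 + 1/100)] = 0.221
- 750 mcg alone: √[3.657 × (1/300 + 1/300)] = 0.156
- 500+750 mcg pooled: √[3.657 × (1/300 + 1/400)] = 0.146

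*Log-linear model,* x = ln(dose + 1). The weighted mean of x is 3.887 and Σn(x − x̄)² = 7805. Slope SE = √(3.657/7805) = 0.02165, and the SE of the log ratio at a dose is x times this:

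- 500 mcg: 6.217 × 0.02165 = 0.135
- 750 mcg: 6.621 × 0.02165 = 0.143

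*3-parameter Emax with ED50 estimated* (local linearisation, log rate ratio −0.3 at 750 mcg):

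| Dose (mcg) | SE, ED50 25 | Ratio to per-arm SE | SE, ED50 100 | Ratio to per-arm SE |
|---|---|---|---|---|
| 50 | 0.170 | 0.77 | 0.155 | 0.70 |
| 100 | 0.147 | 0.67 | 0.171 | 0.77 |
| 250 | 0.134 | 0.61 | 0.147 | 0.67 |
| 500 | 0.135 | 0.61 | 0.134 | 0.61 |
| 750 | 0.137 | 0.88 | 0.137 | 0.88 |

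At 500 and 750 mcg the fair comparator is the planned pool, 0.146, not the stand-alone 500 mcg ratio. The model SE is 0.134–0.143, that is 92–98% of the pooled SE. At 50–250 mcg, where nothing is pooled, the Emax SE is 61–77% of the per-arm SE.

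*Equal arms of 157.* The per-arm SE is 0.216 and the pooled SE 0.187. The Emax SE at 50–750 mcg is 72–89% of the per-arm SE for the same two ED50 values. Under equal variance, μ and k cancel from all these ratios.

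*How far to trust the Emax figures.* By the same linearisation the SE of ED50 is 58 when ED50 is 25, and 233 when ED50 is 100, about 2.3 times the parameter in each case. With a log rate ratio of −0.1 it is about 7 times. ED50 is barely identified, so these SEs are indicative only. A 4-parameter Emax gains less: its SE is 94–97% of the per-arm SE at 750 mcg, and 97% at 12.5 mcg for ED50 25.

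**The case against.** The strongest reply is that this is a modelling preference. The objective also names efficacy, which per-dose ratios serve directly. The SAP does not fit a curve to every endpoint under this objective: pre-bronchodilator FEV1 and change from hospital discharge have none either. The pool already recovers much of the precision at the top doses, and dose/exposure-response work on exacerbations is foreseen. All of this stands. It limits the size of the point, but it does not supply an unconditional dose-response estimate for exacerbations.

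Four stronger readings are tempting and are not supported:

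- **That the analysis is purely arm by arm, or that no dose response is planned.** The pools in 7.2.1.1 and 7.2.2.1 and the conditional work in Section 11 and Appendix 9 contradict this.
- **That a model is worth about 2.7 times the information.** That figure, (0.221/0.135)², takes the stand-alone 500 mcg ratio as comparator and ignores the pool. Against the pool it is (0.146/0.135)² ≈ 1.17.
- **That the ratios come from separate posteriors.** Section 7.2.1.1 specifies one negative binomial model, so the dose ratios share a placebo rate and a joint posterior.
- **That the missing curve causes selection of the best arm at Interim Analysis 2.** Dose adaptation there rests on the FEV1 model (7.1.2). The exacerbation futility rule names 750 mcg, and its option to use another arm is separate wording in 3.1.1.1 that a dose-response model would leave untouched.

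**Conclusion.** The point holds as a gap between objective and analysis. Two endpoints listed under a dose-response objective have per-dose ratios and one two-dose pool, and no dose-response estimate that is certain to be made and reported in the CSR. It does not invalidate the planned estimates, which should stay.

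The main gain from a model is an answer to the stated question. The precision gain is modest at 500–750 mcg and larger at 50–250 mcg. These sizes rest on an assumed rate, dispersion and mock-shell allocation, and on a correctly specified monotone curve. The direction is sound; the size is uncertain. This is a cheap improvement worth making.

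**What to change.** Keep the per-arm and pooled 500+750 mcg estimates as planned. Add to both 7.2.1.1 and 7.2.2.1 a supportive dose-response model, fitted whatever the other results show:

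- Dose enters on the log-rate scale (negative binomial) and the log-hazard scale (Cox), through the log-linear form with offset 1 and, where it converges, the 3-parameter Emax. Both forms are already in 7.1.2.
- Report for each dose the ratio to placebo, its 95% HPD interval and the posterior probability that the ratio is below 1, together with the fitted curve.
- Produce these at SAC and, for the rate, also at Interim Analysis 2. The End of Treatment analysis need not carry them, since Appendix 11 reserves even the FEV1 dose-response tables for SAC.
- Show the per-arm estimates on the same plot as a check on the shape.

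The cost is SAP wording, one additional model and a small set of displays per endpoint, with no new data. The drawback is reliance on a monotone dose shape with an ED50 that may be poorly identified. That is why the model should be supportive and read against the per-arm results.

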7.2.1.2. Subgroup analyses

A subgroup analysis of exacerbation rate by Index exacerbation severity will be performed by including a treatment-by-severity term in the model.

7.2.1.3. Exploratory analyses

A summary of exacerbation rate by the following groups will be presented and, if feasible, a subgroup analyses may be performed:

- Index exacerbation type (New or Relapse)
- Number of exacerbations in previous 12 months (0, 1 or ≥ 2).

7.2.2. Time to next exacerbation

Time to next (on-treatment) exacerbation following index exacerbation during the 12-Week Treatment Period is defined as time from the date of randomisation until the date of onset of the first exacerbation whilst on study treatment. Participants who did not have an exacerbation whilst on study treatment will be censored at the date of their last dose of study treatment.

Time to next (on-or off-treatment) exacerbation during the 12-Week Treatment Period is defined as time from the date of randomisation until the date of onset of the first exacerbation occurring up to Day 84. Participants who have not had an exacerbation during the 12-Week Treatment Period will be censored at Day 84 or the date of study withdrawal, for participants who withdrew from the study prior to Day 84.

Time to next exacerbation following cessation of study treatment is defined as time from the date of last dose of study treatment until the date of onset of the next exacerbation whilst off study treatment during the 12-Week Follow Up Period. Participants who have not had an exacerbation off-treatment will be censored at the date of their last follow up assessment.

Time to next exacerbation will be analysed by severity, as follows:

Endpoint	Time period
Time to next (on-treatment) exacerbation, summarised by: 
 • Moderate/severe exacerbations • All (mild, moderate and severe) exacerbations 	12-Week Treatment Period
Time to next (on-or off-treatment) exacerbation, summarised by: 
 • Moderate/severe exacerbations • All exacerbations 	12-Week Treatment Period
Time to next exacerbation following cessation of treatment, summarised by: 
 • Moderate/severe exacerbations 	12-Week Follow Up Period

Refer to Section [13.5](#) for further details regarding the length of time derivation

7.2.2.1. Statistical analyses

Time to next exacerbation will be analysed using a Bayesian Cox proportional hazards model with the “Efron” method for handling ties.

Kaplan-Meier (KM) estimates of the probability of exacerbation will also be presented.

Non-informative priors will be used for all modelling parameters. Wherever possible conjugate priors will be utilised.

The hazard ratio and corresponding 95% HPD credible intervals for each nemiralisib dose versus placebo will be presented. The probability that the true hazard ratio is less than 1, in addition to other values appropriately selected based on the data, will be presented.

Based on pharmacological predictions, the 500 mcg and 750 mcg doses are expected to result in similar levels of target inhibition and thus potentially translate to similar clinical benefit, therefore an estimate of hazard ratio for pooled data from 500 mcg plus 750 mcg nemiralisib doses versus placebo will also be presented.

7.2.2.2. Subgroup analyses

A subgroup analysis of time to exacerbation by Index exacerbation severity will be performed by including a treatment-by-severity term in the model.

7.2.3. Change from baseline in Clinic Visit trough FEV₁

Change from baseline in clinic visit trough FEV₁ at Day 14, 28, 56 measured post-bronchodilator is defined as:

FEV₁ measured prior to dosing and post-bronchodilator on Day X – Post-bronchodilator Baseline FEV₁

Where Day X is Day 14, 28, and 56.

Change from baseline in clinic visit trough FEV₁ at Day 14, 28, 56, 84 measured pre-bronchodilator is defined as:

FEV₁ measured prior to dosing and pre-bronchodilator on Day X – Pre-bronchodilator Baseline FEV₁

Where Day X is Day 14, 28, 56, and 84.

7.2.3.1. Statistical Analyses

Change from baseline in Clinic Visit trough FEV₁ measured post-bronchodilator will be analysed using a dose response model and repeated measures analysis as described for the primary endpoint in Section [7.1.2](#).

Change from baseline in Clinic Visit trough FEV₁ measured pre-bronchodilator will be analysed using a repeated measures analysis as described in Section 7.1.2

7.2.3.2. Subgroup analyses

A subgroup analysis of change from baseline in clinic visit trough FEV₁ by index exacerbation severity will be performed.

7.2.4. Change from hospital discharge in clinic visit trough FEV₁

Change from hospital discharge in clinic visit trough FEV₁ will be derived only for participants who were hospitalised for their index exacerbation and who have been subsequently discharged.

Change from hospital discharge in clinic visit trough FEV₁ measured post-bronchodilator is defined as:

FEV₁ measured prior to dosing and post-bronchodilator on Day X – FEV₁ measured post-bronchodilator and prior to dosing on day of hospital discharge.

Where Day X is 14, 28, 56 and 84.

Change from hospital discharge in clinic visit trough FEV₁ measured pre-bronchodilator is defined as:

FEV₁ measured prior to dosing and pre-bronchodilator on Day X – FEV₁ measured prior to dosing and post-bronchodilator on day of hospital discharge.

Where Day X is 14, 28, 56 and 84.

Note, as per Section 5.1 of the Protocol, if discharge takes place between Day 11 and Day 17 (inclusive), the assessments planned for Day 14 may be completed on the day of discharge. In these cases, for this endpoint only, the FEV₁ assessment will be assigned the hospital discharge assessment and the Day 14 assessment will be missing. Refer to Section 13.2.1.1 for further details.

In addition, if discharge takes place after Day 14, the Day 14 assessment will be missing for this analysis.

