13.11.6.3. Efficacy tables for End of Treatment Interim Analysis and SAC

Efficacy: Tables					
No.	Population	IDSL / Example Shell	Title	Programming Notes	Deliverable [Priority]
Change from Baseline in Clinic Visit trough FEV₁					
2.1.	MITT	Example 3	Summary of FEV ₁ (L)	Include pre- and post-bronchodilator	EOT, SAC
2.2.	MITT	Example 3	Summary of FEV ₁ (L) by Index Exacerbation Severity	Include pre- and post-bronchodilator Include additional row for hospital discharge visit for Severe group	EOT, SAC

Efficacy: Tables					
No.	Population	IDSL / Example Shell	Title	Programming Notes	Deliverable [Priority]
2.3.	MITT	Example 3	Summary of Change from Baseline in FEV ₁ (L)	Include pre- and post-bronchodilator	EOT, SAC
2.4.	MITT	Example 3	Summary of Change from Baseline in FEV ₁ (L) by Index Exacerbation Severity	Include pre- and post-bronchodilator. Include additional row for hospital discharge visit for Severe group	EOT, SAC
2.5.	MITT	Example 26	Statistical Analysis of Change from Baseline in FEV ₁ (L) at Day 14 Measured Post-bronchodilator (Dose Response Model)		SAC
2.6.	MITT	Example 26	Statistical Analysis of Change from Baseline in FEV ₁ (L) at Day 28 Measured Post-bronchodilator (Dose Response Model)		SAC
2.7.	MITT	Example 26	Statistical Analysis of Change from Baseline in FEV ₁ (L) at Day 56 Measured Post-bronchodilator (Dose Response Model)		SAC
2.8.	MITT	Example 26	Statistical Analysis of Change from Baseline in FEV ₁ (L) at Day 84 Measured Post-bronchodilator (Dose Response Model)		SAC
2.9.	MITT	Example 26	Subgroup Analysis of Change from Baseline in FEV ₁ (L) at Day 14 Measured Post-bronchodilator by Index Exacerbation Severity: Moderate (Dose Response Model)		SAC
2.10.	MITT	Example 26	Subgroup Analysis of Change from Baseline in FEV ₁ (L) at Day 14 Measured Post-bronchodilator by Index Exacerbation Severity: Severe (Dose Response Model)		SAC
2.11.	MITT	Example 26	Subgroup Analysis of Change from Baseline in FEV ₁ (L) at Day 28 Measured Post-bronchodilator by Index Exacerbation Severity: Moderate (Dose Response Model)		SAC
2.12.	MITT	Example 26	Subgroup Analysis of Change from Baseline in FEV ₁ (L) at Day 28 Measured Post-bronchodilator by Index Exacerbation Severity: Severe (Dose Response Model)		SAC

Efficacy: Tables					
No.	Population	IDSL / Example Shell	Title	Programming Notes	Deliverable [Priority]

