2.13.	MITT	Example 26	Subgroup Analysis of Change from Baseline in FEV ₁ (L) at Day 56 Measured Post-bronchodilator by Index Exacerbation Severity: Moderate (Dose Response Model)		SAC
2.14.	MITT	Example 26	Subgroup Analysis of Change from Baseline in FEV ₁ (L) at Day 56 Measured Post-bronchodilator by Index Exacerbation Severity: Severe (Dose Response Model)		SAC
2.15.	MITT	Example 26	Subgroup Analysis of Change from Baseline in FEV ₁ (L) at Day 84 Measured Post-bronchodilator by Index Exacerbation Severity: Moderate (Dose Response Model)		SAC
2.16.	MITT	Example 26	Subgroup Analysis of Change from Baseline in FEV ₁ (L) at Day 84 Measured Post-bronchodilator by Index Exacerbation Severity: Severe (Dose Response Model)		SAC
2.17.	MITT	Example 11	Sensitivity Analysis of Change from Baseline in FEV ₁ (L) Measured Post-bronchodilator (Repeated Measures Model)		EOT, SAC
2.18.	MITT	Example 11	Sensitivity Analysis of Change from Baseline in FEV ₁ (L) Measured Post-bronchodilator by Index Exacerbation Severity (Repeated Measures Model)		EOT, SAC
Change from Hospital Discharge in Clinic Visit trough FEV₁					
2.19.	MITT	Example 3	Summary of Change from Hospital Discharge in FEV ₁ (L)	Include pre- and post-bronchodilator	SAC
2.20.	MITT	Example 11	Statistical Analysis of Change from Hospital Discharge in FEV ₁ (L) Measured Post-bronchodilator (Repeated Measures Model)		SAC
2.21.	MITT	Example 11	Statistical Analysis of Change from Hospital Discharge in FEV ₁ (L) Measured Pre-bronchodilator (Repeated Measures Model)		SAC
Change from Day 84 in Clinic Visit trough FEV₁					
2.22.	MITT	Example 3	Summary of Change from Day 84 in FEV ₁ (L)	Include pre- and post-bronchodilator	SAC

Efficacy: Tables					
No.	Population	IDSL / Example Shell	Title	Programming Notes	Deliverable [Priority]
2.23.	MITT	Example 11	Statistical Analysis of Change from Day 84 in FEV ₁ (L) Measured Post-bronchodilator (Repeated Measures Model)		SAC
2.24.	MITT	Example 11	Statistical Analysis of Change from Day 84 in FEV ₁ (L) Measured Pre-bronchodilator (Repeated Measures Model)		SAC
2.25.	MITT	Example 11	Subgroup Analysis of Change from Day 84 in FEV ₁ (L) Measured Post-bronchodilator by Index Exacerbation Severity (Repeated Measures Model)		SAC
2.26.	MITT	Example 11	Subgroup Analysis of Change from Day 84 in FEV ₁ (L) Measured Pre-bronchodilator by Index Exacerbation Severity (Repeated Measures Model)		SAC
Rate of Exacerbations					

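### SAP 7.2.4 subtracts a post-bronchodilator discharge value from a pre-bronchodilator FEV₁, which lowers the within-arm change; separately, the pre-bronchodilator change-from-baseline model promised in 7.2.3.1 has no final table

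*SAP*

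**What the plan says.** **Change from discharge.** Section 2.1 lists as a secondary endpoint "Change from hospital discharge in clinic visit trough FEV₁ measured pre- and post-bronchodilator at Days, 14, 28, 56, and 84", in participants hospitalised for the index event. Section 7.2.4 then defines two versions. The post-bronchodilator version is post minus post. The pre-bronchodilator version is FEV₁ "measured prior to dosing and pre-bronchodilator on Day X – FEV₁ measured prior to dosing and post-bronchodilator on day of hospital discharge".

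**Other pre-bronchodilator changes.** Section 7.2.3 defines change from baseline as FEV₁ "measured prior to dosing and pre-bronchodilator on Day X – Pre-bronchodilator Baseline FEV₁". Section 7.3.1 does the same against the Day 84 pre-bronchodilator value.

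**Discharge spirometry.** The change-from-baseline endpoint in Section 2.1 is "measured pre- and post-bronchodilator at Days 14, 28, 56, and 84", and the same entry continues "and at hospital discharge (only for participants who are hospitalized for the index exacerbation". In 13.11.6.3, Tables 2.2 and 2.4 call for both pre- and post-bronchodilator results, with the note "Include additional row for hospital discharge visit for Severe group".

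**Model for pre-bronchodilator change from baseline.** Section 7.2.3.1 says that this change "measured pre-bronchodilator will be analysed using a repeated measures analysis as described in Section 7.1.2". (The repeated-measures model is in fact described in 7.1.3.) In the list for the end-of-treatment analysis and the final analysis (SAC), the repeated-measures tables for change from baseline, 2.17 and 2.18, are both "Measured Post-bronchodilator (Repeated Measures Model)".

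**The concern.** A change score whose two terms are taken under different bronchodilator conditions does not measure change alone. It combines the change since discharge with the acute response to bronchodilator at discharge. A programmer who follows 7.2.4 exactly would produce an endpoint that is not the one named in Section 2.1. Table 2.21 uses Example Shell 11, which shows the adjusted change in each arm as well as the difference from placebo, so the displaced level would be reported under a label that hides its cause.

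The second matter is a mismatch between text and display list. Pre-bronchodilator change from baseline at Day 84 is named as a secondary endpoint and a model is promised for it. That model has tables at both interim analyses and none at the end.

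**Working it through.** The plan states no figure on this point, so there is nothing to reproduce. The check is a comparison of definitions, an identity, and an illustration on assumed values.

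**1. Definitions in the current plan**

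| Endpoint | Section | Day X term | Reference term |
|---|---|---|---|
| Change from baseline, post | 7.1.1, 7.2.3 | post | post |
| Change from baseline, pre | 7.2.3 | pre | pre |
| Change from discharge, post | 7.2.4 | post | post |
| **Change from discharge, pre** | **7.2.4** | **pre** | **post** |
| Change from Day 84, post | 7.3.1 | post | post |
| Change from Day 84, pre | 7.3.1 | pre | pre |

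One row does not match. The superseded versions of the plan in the same file suggest a carry-over. The oldest subtracts a post-bronchodilator reference for all three pre-bronchodilator changes. The next corrects baseline and Day 84 but leaves discharge, and the current text repeats it. This is evidence of intent only; the error is in the current 7.2.4.

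**2. Identity**

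Let R = post(discharge) − pre(discharge). Then

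pre(X) − post(discharge) = [pre(X) − pre(discharge)] − R.

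The mean within each arm is therefore lower than the like-for-like change by exactly the mean of R in that arm.

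**3. Size of the shift**

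The documents do not give R. Over an assumed range:

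| Assumed mean R (mL) | Recorded change in an unchanged patient (mL) |
|---|---|
| 50 | −50 |
| 100 | −100 |
| 150 | −150 |
| 200 | −200 |

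**4. Contrast with placebo**

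By the identity, the unadjusted difference between arms equals the like-for-like difference minus (mean R in active − mean R in placebo). If R has the same mean in both arms, the contrast is unchanged. Illustration: with a like-for-like difference of 50 mL and R 30 mL smaller on active (both assumed), the recorded difference is 50 − (−30) = 80 mL.

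**5. Precision**

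The variance becomes Var(change) + Var(R) − 2Cov(change, R). In a simulation with a like-for-like SD of 0.226 L and an independent R with SD 0.100 L (both assumed), √(0.226² + 0.100²) = 0.247 L. The residual SD after adjustment for the discharge value rose from 0.220 to 0.237 L. A positive covariance would reduce or reverse this, and the documents give none of these quantities.

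**6. Where pre-bronchodilator change from baseline is modelled**

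| Analysis | Repeated-measures tables, pre-bronchodilator |
|---|---|
| Interim Analysis 1 | 2.10 and 2.12 |
| Interim Analysis 2 | 2.18 and 2.20 |
| End of treatment and SAC | none |

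In the last list, the dose-response tables 2.5 to 2.16 and the repeated-measures tables 2.17 and 2.18 are all post-bronchodilator. Tables 2.3 and 2.4 still summarise the pre-bronchodilator change.

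**The case against.** The strongest reply is that little rests on this endpoint. It is one of two versions of a secondary endpoint, covers hospitalised participants only, and under 7.2.4.1 is modelled only if numbers suffice. It has no part in the primary analysis or the futility rules, and its post-bronchodilator counterpart is correctly defined. All of that stands, and it limits the severity.

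A reader might infer that the treatment effect itself is biased by 50 to 200 mL, or is swamped relative to the 75 mL in 7.1.2. The documents do not support that. The 75 mL belongs to the primary post-bronchodilator analysis, where it is an improvement threshold reported alongside the difference from placebo. The shift here is in the within-arm level, and a common shift cancels in the contrast. The 50 to 200 mL range is also an assumption.

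It can further be said that the model adjusts for baseline by Day. If that covariate is the discharge value being subtracted, the adjusted difference is the same whether or not it is subtracted. That is correct, but such a model still adjusts for the post-bronchodilator value and need not remove an arm difference in R. With the assumed inputs of the simulation (slope 0.9, SD of pre-bronchodilator discharge FEV₁ 0.45 L, SD of R 0.10 L), the 30 mL imbalance gives 50 + 0.9 × 0.45²/(0.45² + 0.10²) × 30 ≈ 76 mL, against 80 mL unadjusted. The plan does not say whether the covariate is the Day 1 or the discharge value, so the extent of any absorption is open. So is the imbalance, for which the documents give no evidence. Changing the reference would also leave it a post-randomisation measurement.

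On the missing table, a reader might infer that this secondary endpoint is not reported at all at the end. It is, descriptively, in Tables 2.3 and 2.4. Pre-bronchodilator repeated-measures tables were on the final list in the oldest version and are absent from the two later ones, so their removal may have been deliberate. In that case 7.2.3.1 is what needs changing.

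**Conclusion.** The definition in 7.2.4 is wrong as written. The within-arm pre-bronchodilator change from discharge in Tables 2.19 and 2.21 is lowered by the mean bronchodilator response at discharge. That follows from the identity alone; its size cannot be taken from the documents. An effect on the contrast with placebo is possible because discharge comes after randomisation, but it requires a response that differs by arm and is not absorbed by adjustment. A loss of precision is plausible but rests on assumed variances.

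The display gap is confirmed in a narrow form: at the end-of-treatment and final analyses no model-based table is listed for pre-bronchodilator change from baseline, although 7.2.3.1 promises the analysis.

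Both should be fixed. Neither touches the primary endpoint or a stopping decision.

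**What to change.** 1. In 7.2.4, change the reference term of the pre-bronchodilator version to the pre-bronchodilator FEV₁ measured before dosing on the day of discharge. This is one word. First confirm against the protocol's schedule, which is not shown here, that this value is collected. If it is not, the pre-bronchodilator discharge entries in Section 2.1 and Tables 2.2 and 2.4 must be reconciled instead.
2. In 7.2.4.1, state which value enters the repeated-measures model as the baseline covariate for this endpoint, and point to 7.1.3, where the model is described.
3. In 13.11.6.3, add the pre-bronchodilator repeated-measures tables for change from baseline, overall and by index exacerbation severity, as SAC deliverables. They use the same model and shell as Tables 2.17 and 2.18 and are already specified for the interims. If their removal was intended, amend 7.2.3.1 to say that this endpoint is only summarised at the final analysis.

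The cost is a short text amendment and at most two further tables. It is best made before the final unblinding, since a later change to an endpoint definition could be read as data-driven.
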